12.1.2 Reporting Serious Adverse Events

Serious is a regulatory definition and is based on subject or event outcome or action criteria usually associated with events that pose a threat to a subject's life or functioning. Seriousness (not severity) serves as the guide for defining the sponsor's regulatory reporting obligations (i.e., to the applicable regulatory authorities). Adverse event severity and seriousness should be assessed independently by investigators.

MIP, as Sponsor of the study, is responsible for reporting relevant SAEs as safety reports to the FDA, Health Canada and other applicable regulatory authorities, and participating Investigators, in accordance with the US Code of Federal Regulations (CFR) Title 21 CFR 312.32 and 312.33, European Clinical Trials Directive, ICH guidelines, Health Canada guidelines, Good Clinical Practice and/or local regulatory requirements.

The Investigator must report all SAEs to MIP designee within 24 hours, by telephone, email or fax, and confirm that the information was received (see Appendix VIII).

A Serious Adverse Event Report (SAER) must be completed by the Investigator or designee and faxed or emailed to MIP's designee within 24 hours after the Investigator first becomes aware of the serious event. A separate SAER will be needed for each reported SAE so that the onset, resolution date causality and outcome can be assessed for each event. Any source documents relevant to the event should be forwarded to MIP's designee with the SAER form. The SAER form must be signed and dated by the Investigator. The Original copy must remain on site with the CRF.

In case of death, a comprehensive narrative report of the case should be prepared by the Investigator and sent to MIP's designee, together with the SAER. If an autopsy is performed, a copy of the autopsy report should be actively sought by the Investigator and sent to the Sponsor or designee as soon as available. A copy of the autopsy report must remain on site with the CRF.

All deaths will be reported as SAEs regardless of their relationship to disease progression and reported via an SAER form from the time of signed informed consent until completion of the follow up period. All other SAEs will be reported until the last day of Week 15 following the last administration of Ultratrace iobenguane I 131, and reported via an SAER form to MIP's designee.

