A new follow-up SAER form will be filled in by the Investigator if important follow-up information (i.e., diagnosis, outcome, causality assessment, results of specific investigations) are made available after submission of the initial form. The follow up SAER must be signed and dated by the Investigator. The follow-up form and any additional source documentation regarding the event will be sent to the sponsor, or designee, as described above.

If a serious medical occurrence or death is reported to the Investigator outside the follow up window, which is believed to be related to the administration of the investigational product, it is the Investigator's responsibility to report this occurrence to MIP's designee. Such occurrences will be reported using a SAER form or other form of communication deemed appropriate by the Investigator and MIP.

Sites must contact MIP's designee to report all SAEs within 24 hours, by telephone, email or fax.

Contact Information in the US, UK and Canada, see Appendix VIII.

Sites must also report all pregnancies, overdoses and extravasations to MIP's designee. In the case of pregnancy, the pregnancy will be followed until the pregnancy outcome is known. The form must be completed and submitted to MIP's designee. Additional information, including source documentation, may be requested as follow up to any pregnancy.

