12.1.4 Data Collection

The Investigator will elicit information through non-leading questioning and examination of the subject about the occurrence of adverse events from the time of informed consent until the Safety Phone Call 16 weeks after the last dose of study drug.

For each event, the following information will be recorded in the subject's records and transcribed onto the AE section of the CRF according to the instructions described below.

- Classification of the Event as serious or non-serious: Classify the event as either serious or non-serious (see definitions in Section 12.1.1).
- Classification of the Event as an adverse event of special interest (AESI): Determine if the event is an AESI (see Appendix VI).
- **Description of Signs or Symptoms**: Whenever possible, record a specific diagnosis for the event. If a diagnosis cannot be made, then record each sign or symptom separately, (e.g., record nausea and vomiting as two events).
- **Onset Date and Time:** Record the date and time the event started (e.g. if a laboratory test is reported as an AE, record the start date as the date of collection of the first lab sample that shows the change.)
- Stop Date and Time: Record the date and time the event resolved.
- **Grade:** Refer to the common terminology criteria for adverse events (CTCAE, version 3).

Relationship to the Study Drug: Make every effort to evaluate the relationship between the study drug and the AE as determined by the investigator per the definitions below:

RelatedThe event is reasonably suspected of a causal relationship to the
study drug and/or causality cannot definitively be ruled out.Not RelatedThe event is definitely due to causes separate from the
administration of the study drug, i.e.,

- documented pre-existing condition
- technical and manual procedural problems
- concomitant medication
- subject's clinical state

• Action Taken with Study Drug:

- 1. Dose not changed (no action taken)
- 2. Dose reduced
- 3. Drug withdrawn
- 4. Not applicable

• Adverse Event Outcome:

- 1. Recovered/ Resolved without sequelae
- 2. Recovered/Resolved with sequelae
- **3.** Not recovered/Not resolved, event is on-going at the end of the AE collection period.
- **4. Death (fatal)** the event description must be the primary cause of death. Disease progression is not considered an acceptable cause of death for purposes of this study.
- 5. Unknown

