7.5.1. Adverse Events

TEAEs are defined as AEs whose onset dates are on or after the first administration of any amount of study drug to the end of 15 weeks after the administration of the last therapeutic dose of iobenguane I 131. If the onset date is incomplete, then assessment will be made based on available information (i.e., comparing available onset month and year). If the onset date is incomplete and assessment could not be made based on the available information (for example, year is missing) then the AE will be considered as TEAE. Events that resolve prior to date of the first dose of study drug will not be considered as TEAEs regardless of completeness of the onset date. In all table summaries, only TEAEs will be presented. All AEs will be presented in listings, regardless of whether they are treatment-emergent.

All adverse events that are neither serious adverse events nor adverse events of special interest reported with start dates on or after the first day of week 16 following the last therapeutic dose will be presented in a summary table and will be included in the listing of all adverse events.

For subjects who discontinue participation in the study due to receiving another anticancer therapy, all adverse events reported with start dates after the initiation date of the new therapy but prior to the last day of week 15 after the last therapeutic dose will be summarized separately. These events will also be included in the overall adverse event summaries. These events will be flagged in the listings of adverse events.

AEs were originally coded according to system organ class and preferred term using MedDRA version 12, and were recoded to MedDRA version 19.1 for analysis. The AE terms were graded for severity according to the Common Terminology Criteria for Adverse Events v3.0 (CTCAE v3).

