7.5.4. Serious Adverse Events

SAEs are any untoward medical occurrences that meet any of the criteria for SAEs as described in the protocol. The number of subjects with at least one Treatment Emergent SAE and the number of subjects under each body system and preferred term will be tabulated by relation to study drug for the Safety Set. All SAEs will be included in the listing of AEs. Two additional listings will be provided: one including all SAEs, and one including all SAEs where the relationship to drug is Related (or is missing).

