7.5.6. All Deaths during the Study

All deaths reported during the study will be reported in a separate listing. This listing will include the period of death (during the efficacy phase or during the follow-up phase), date of death, relative day of death relative to the first therapeutic dose, and the cause of death.

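### From Week 16 after the last dose, the SAP tabulates non-serious events but only lists serious non-AESI events, and it leaves two AESI lists unreconciled

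*SAP*

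**What the plan says.** **Tables.** SAP 7.5.1 ends the treatment-emergent window 15 weeks after the last therapeutic dose and then states: "In all table summaries, only TEAEs will be presented". All adverse events, whenever they start, go into listings. The one exception for later onset is a summary table (planned Table 14.3.1.1.1) that begins with Week 16 and covers "All adverse events that are neither serious adverse events nor adverse events of special interest reported with start dates on or after the first day". For serious events, SAP 7.5.4 tabulates "The number of subjects with at least one Treatment Emergent SAE" and lists all SAEs without a time limit.

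**Collection.** Protocol 12.1.2 keeps deaths in the SAE system until follow-up is complete: "All deaths will be reported as SAEs regardless of their relationship to disease progression". Other SAEs stop earlier: "All other SAEs will be reported until the last day of Week 15 following the last administration of Ultratrace iobenguane I 131". A further route stays open for occurrences attributed to the product, which the investigator must report: "If a serious medical occurrence or death is reported to the Investigator outside the follow up window, which is believed to be related".

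**Deaths.** SAP 7.5.6 says: "All deaths reported during the study will be reported in a separate listing". That listing covers the efficacy and follow-up phases and gives the cause. Planned Table 14.3.2.1 is titled for the 12-month assessment period only. Planned Listing 16.2.7.3 covers fatal adverse events without a time limit.

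**AESIs.** SAP 7.5.8 summarizes the events indicated in Protocol 12.1.2.1 with onset beyond 16 weeks. The protocol's list is in Appendix VI, although 12.1.2.1 itself cites Appendix IV, which holds the questionnaires. SAP Appendix 2 is a different list, and the change table in SAP section 9 describes it as updated to carry the terms for the analysis.

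**The concern.** The plan follows subjects for five years after a radiotherapeutic, with late toxicity as a stated interest. A late-event table that shows non-serious events and leaves out serious ones gives a reader of the tables alone the wrong impression of the late period. The SAE table does not fill the gap because it stops at Week 15.

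The AESI summary should be the main late-toxicity output, but its content depends on which of two lists the programmer uses. The two problems interact: a late serious event that is on one list and not on the other moves between a table and a listing according to that choice.

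**Working it through.** The SAP states no figure on this point that could be reproduced. The check applies its rules to each type of event.

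**Inputs.** The week windows in Protocol 11.5.18 and SAP Appendix 1 make Week k run from Day 7(k-1)+1 to Day 7k for k of 2 or more. Counted from the last therapeutic dose, Week 15 ends on Day 7 x 15 = 105. Week 16 runs from Day 106 to Day 112. Read literally, beyond 16 weeks starts on Day 113.

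**Where each event goes under SAP 7.5.1, 7.5.4 and 7.5.8:**

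| Onset after last dose | Non-serious, non-AESI | Serious, non-AESI | AESI |
|---|---|---|---|
| To Day 105 | TEAE tables | TEAE tables and Table 14.3.1.3 | TEAE tables (and 14.3.1.3 if serious) |
| Days 106-112 | Table 14.3.1.1.1 | Listings only | Listings only, on a literal reading |
| From Day 113 | Table 14.3.1.1.1 | Listings only | Table 14.3.1.6 |

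The grade 3/4 tabulations do not help, because SAP 7.5.3 limits them to TEAEs. One exception is possible: the hematologic summary in SAP 7.5.5 includes SAEs and states no time limit of its own, so a late hematologic SAE might enter Table 14.3.1.4 if the general rule in 7.5.1 is not applied to it. The title of Table 14.3.1.1.1 calls events after Week 15 treatment-emergent, which contradicts the definition in 7.5.1, and it does not repeat the exclusion of SAEs and AESIs.

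**Which events fall in the middle column.** Routine reporting of non-fatal SAEs stops at Week 15. What remains is (a) deaths, which are SAEs until the end of follow-up, and (b) late serious occurrences reported as related and not classed as AESIs. Group (a) is counted in disposition (SAP 7.2.1) and overall survival (SAP 7.4.11), but neither is by event term.

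**The two AESI lists.** Counting distinct entries:

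- Protocol Appendix VI has 106 terms and SAP Appendix 2 has 53.
- 28 are identical in wording. Of the other 53 - 28 = 25 SAP terms, some are near-synonyms of protocol terms (erectile dysfunction, xerostomia) and some are new (alopecia, oligospermia, salivary gland dysfunction).
- Cardiac/vascular has 17 entries in the protocol and 4 in the SAP. Eyes and Ears has 6 and 0. Heart failure is only in the protocol list.

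**Interaction.** Take a serious heart failure starting after Day 112. Under Appendix VI it is an AESI and enters Table 14.3.1.6. Under Appendix 2 it is a serious non-AESI event and is only listed. A non-serious cataract with the same onset is tabulated either way, as an AESI or as a late event. The choice of list therefore changes the counts in both tables, but removes an event from all tables only when the event is serious.

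**The case against.** **Late serious events may be few and partly covered.** Protocol 12.1.2.1 also asks for expedited reporting of unlisted events that are medically significant and possibly related, and SAP 7.5.8 lets terms be added before database lock. Late related SAEs may therefore reach the AESI table. This stands, and it is why no number is claimed for them.

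**Deaths are well covered individually.** The listing in 7.5.6 gives phase, date and cause, and Listing 16.2.7.3 has no 12-month limit. This stands. A reader might infer that late deaths go unreported; the documents do not support that. Nor is it certain that the rule in Protocol 12.1.4, "Disease progression is not considered an acceptable cause of death for purposes of this study", governs late deaths, because that section describes collection up to the 16-week safety call.

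**A count of late deaths is tempting but measures something else.** Assume constant hazard, a cut-off at Day 189 (84 + 105), 58 to 75 treated subjects and the 5-year survival of 40% to 85% cited in Protocol 7.1 and 7.2. The expected deaths between the cut-off and Day 1,826 then run from 58 x (0.85^(189/1826) - 0.85) = 58 x 0.1333 = 7.7 to 75 x (0.40^(189/1826) - 0.40) = 75 x 0.5095 = 38.2. These are all late deaths, including those due to AESIs, and all are listed and counted in overall survival. They are not events lost to the report. The figures come from other cohorts, and Protocol 7.1 also says survival in this setting is often 24 months or less, so the range is not a bound.

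**The SAP is not silent on the AESI list.** A reader might infer that nothing indicates which list applies. In fact 7.5.8 indicates the protocol list and the change table indicates Appendix 2. Protocol 13.5 allows the final SAP to change the planned analysis, so a broad collection list and a narrower analysis list could coexist. What stands is that the two pointers conflict and no sentence resolves them.

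**The Week 16 gap depends on the reading.** Protocol 12 starts AESI collection 16 weeks after the last dose, which may itself mean about Day 112. SAP 7.5.8 also defines AESIs by reporting beyond 16 weeks, so a non-serious event of an AESI term that starts and is reported in Week 16 may not count as an AESI and would enter the late-event table. Only serious events, or those reported later, could be missed. This stands as a limit on the point.

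**Listings are defensible for partly collected data.** Late SAE counts cannot be complete incidences. That calls for a footnote; it does not justify tabulating only the non-serious part.

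**Conclusion.** The concern holds as a reporting asymmetry that should be corrected. Read as written, SAP 7.5.1 and 7.5.4 put a serious non-AESI event with onset from Week 16 in listings only, except possibly a hematologic one, and a non-serious non-AESI event in a table. What is missing is a summary by event term. Individual cases and the total of deaths remain visible. The number affected cannot be derived from the documents.

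The AESI list is a real conflict between two pointers, with 106 against 53 terms and 28 in common by exact wording. The boundary mismatch covers at most 7 days (Days 106-112) and affects only some AESIs, on a literal reading.

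The conclusion assumes that the general rule on tables in 7.5.1 applies throughout section 7.5, and that the protocol's clause on related events outside the follow-up window includes the period after Week 15.

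**What to change.** 1. Extend Table 14.3.1.1.1 to all reported adverse events with onset from Week 16, with separate rows for SAEs (including fatal events by term) and AESIs. Add a footnote that after Week 15 non-AESI SAEs were collected only if fatal or reported as related, so the counts are not complete incidences. Amend the sentence "In all table summaries, only TEAEs will be presented" to allow this table, and drop the treatment-emergent label from its title.
2. Name in SAP 7.5.8, before database lock, the one AESI list that governs the summary. Report any event collected as an AESI under Protocol Appendix VI but outside that list in the late-event table. Combining the two lists is one option; the essential step is to name one.
3. Use one boundary, the first day of Week 16, in both 7.5.1 and 7.5.8.
4. Retitle Table 14.3.2.1 to cover all deaths, as 7.5.6 says.

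The cost is SAP wording, one enlarged table and two new titles, with no new data collection. The drawback is slightly more table work and late SAE counts that are incomplete by design, which the footnote discloses.

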7.5.2. Relationship of Adverse Events to Study Drug

TEAEs will be summarized by relationship to study drug (related/not related). If a subject experienced more than one TEAE within a preferred term or system organ class, the more related TEAE will be presented at each level of summarization. If the relationship is missing, then 'Related' will be used for the summary table, and the relationship in the listing will be presented as missing.

7.5.3. Severity of Adverse Event

The number of subjects with AEs and number of subjects under each system organ class and preferred term will be summarized by severity (grade 1 = mild AE, grade 2 = moderate AE, grade 3 = severe AE, grade 4 = life-threatening or disabling AE, grade 5 = death related to AE). If a subject experienced more than one TEAE within a preferred term or system organ class, the TEAE with the most extreme severity will be presented at each level of summarization. If the severity is missing, then 'grade 3' will be used for the summary table, and the severity in the listing will be presented as missing. The summary table will also include a row indicating the number of missing severity ratings.

Separate from the listing of all AEs, additional summary tabulations will present all grade 3/4 TEAEs, and all grade 3/4 TEAEs where the relationship to drug is related (or is missing).

A horizontal bar chart will be created using most frequent AEs ($\geq 20\%$) experienced by subjects by incidence rate. The bars for AEs will be sorted in descending sequence of the incidence rate, e.g., an AE with the highest incidence rate will appear at the top; an AE with the second highest incidence rate will appear next and so on. This chart will be limited to TEAEs.

7.5.4. Serious Adverse Events

SAEs are any untoward medical occurrences that meet any of the criteria for SAEs as described in the protocol. The number of subjects with at least one Treatment Emergent SAE and the number of subjects under each body system and preferred term will be tabulated by relation to study drug for the Safety Set. All SAEs will be included in the listing of AEs. Two additional listings will be provided: one including all SAEs, and one including all SAEs where the relationship to drug is Related (or is missing).

7.5.5. Hematologic Adverse Events

AEs of a hematologic nature are of particular interest in this study. However, similar hematologic AEs are often coded under different preferred terms (e.g., ‘leukopenia’ and ‘white blood cell count decreased’). An additional summary of hematologic events categorized as either grade 3, grade 4, or as SAEs, combining such similar preferred terms, will be presented. The following preferred terms are classified as hematologic AEs. This list may be updated prior to database lock and analysis if additional preferred terms are reported.

- ‘Anaemia’
- ‘Anaemia macrocytic’
- ‘Febrile neutropenia’
- ‘Haemolytic anaemia’
- ‘Haematocrit decreased’
- ‘Haemoglobin decreased’
- ‘International Normalised Ratio Increased’
- ‘Leukopenia’
- ‘Leukocytosis’
- ‘Lymphopenia’
- ‘Lymphocyte count decreased’
- ‘Lymphocyte percentage decreased’
- ‘Monocyte count decreased’
- ‘Monocyte count increased’
- ‘Eosinophil count decreased’
- ‘Neutropenia’
- ‘Neutrophil count increased’
- ‘Neutrophil percentage increased’
- ‘Pancytopenia’
- ‘Red blood cell count decreased’
- ‘Thrombocytopenia’
- ‘Platelet count decreased’
- ‘Platelet count increased’
- ‘Mean platelet volume decreased’
- ‘Neutrophil count decreased’

- ‘Neutrophil percentage decreased’
- ‘White blood cell count decreased’
- ‘Prothrombin time prolonged’

7.5.6. All Deaths during the Study

All deaths reported during the study will be reported in a separate listing. This listing will include the period of death (during the efficacy phase or during the follow-up phase), date of death, relative day of death relative to the first therapeutic dose, and the cause of death.

7.5.7. Adverse Events Resulting in a Discontinuation in Study Treatment

Adverse events where the action taken is a discontinuation of study treatment will be reported in a separate listing.

7.5.8. Adverse Events of Special Interest

Adverse Events of Special Interest (AESIs) are defined in the protocol as being any serious or nonserious event of scientific or medical concern specific to iobenguane I 131 reported beyond 16 weeks after the last therapeutic dose of study drug, and have been associated with long term radiation toxicity. This list will be updated prior to database lock and analysis if additional preferred terms are reported. AESIs are to be captured in the safety database along with SAEs. A separate analysis will be performed for AESIs outside of the analyses already defined for SAEs. Each AESI is to be written up in the Clinical Study Report (CSR) (Section 10.3.3: Narratives of Deaths and Other Serious and Certain Other Adverse Events).

The events of special interest indicated in Protocol [Section 12.1.2.1](#) with an onset beyond 16 weeks after the last therapeutic dose of study drug will be summarized and reported in a separate listing.

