9.3 Study Duration

Subjects will attend study visits from the time of signed informed consent through 12 months (efficacy portion) and a 5 year follow-up period after the first Therapeutic Dose of Ultratrace iobenguane I 131. Subjects will be monitored for AE/SAE and Adverse Events of Special Interest (including post radiation toxicity) as described in Section 12. Subjects may undergo additional assessments to confirm response, or as part of institutional standard of care during long-term follow-up. Figure 1 outlines the study period; a more extensive summary of study procedures is given in the Schedule of Procedures (Appendix VII).

FIGURE 1: STUDY DURATION

Signed informed consent, subject enters study Eligibility/dosimetry study Imaging Dose (3 to 6 mCi) of Ultratrace iobenguane I 131 administered within 30 days of first therapeutic dose followed by three I 131 whole body scans to confirm uptake and to determine dosimetry First Therapeutic Dose of Ultratrace iobenguane I 131 administered day 0 I 131 scan within seven days post first therapeutic infusion to assess biodistribution Safety visit 6 weeks post-first Therapeutic Dose Objective tumor response assessments 3 months post-Therapeutic Dose and prior to the second Therapeutic Dose Second Therapeutic Dose Ultratrace iobenguane I 131 administered starting at month 3, at least 12 weeks after the first Therapeutic Dose. I 131 scan within seven days after second Therapeutic Dose Safety visit 6 weeks post second Therapeutic Dose Tumor response assessments, tumor markers (every two weeks through week 24 and monthly from month 7-12), physical exam at months 3 (prior to the second Therapeutic Dose, if administered), 6, 9 and 12 Subject completes regularly scheduled study visits at month 12 Long-term follow-up for adverse events of special interest, overall survival, tumor markers and disease status (inc. clinical benefit) through year 5

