10.2 Dose Modification

Dosimetry will be calculated to confirm that the protocol-specified two administrations of 500 mCi (or 8 mCi/kg for subjects weighing 62.5 kg or less) of Ultratrace iobenguane I 131 does not exceed the specified absorbed dose levels (23 Gy to the kidney, 17.5 Gy to the lungs and 30 Gy
to the liver) over the entire treatment (two therapeutic doses). Additionally, subjects must have recovered from treatment side effects experienced during the initial dose and prior to administration of the second dose. Dose modification, if required, may be based on subject's body weight, estimated renal, hepatic or lung absorbed dose or hematological toxicity. Similarly, the Principal Investigator or designee may modify second dose scheduling, in consultation with the study medical monitor, due to medical condition and/or other logistic or personal reasons. In any case this delay of second therapeutic dose should not exceed 24 weeks from the first therapeutic dose. Specifically, if the total dose requires downward adjustment resulting from the dosimetry calculation, then both the first and second Treatment Doses will be decreased equally.

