10.2.2 Dose modification for hematologic toxicity

The subject's hematologic values must return to baseline levels prior to administration of the second Therapeutic Dose. The administration of the second Therapeutic Dose may be delayed for up to 4 - 12 weeks (i.e., 16 - 24 weeks following administration of the first Therapeutic Dose) to allow for adequate hematologic recovery. If recovery to baseline levels has not occurred within 24 weeks following the initial Therapeutic Dose, the subject should be discontinued from the study.

Additionally, if the subject has experienced:

- Febrile neutropenia (temperature \geq 38.5° C and ANC <1,000/µL); or
- CTCAE Grade 3 thrombocytopenia with active bleeding; or
- CTCAE Grade 4 hematological toxicity >1 week duration at any time following administration of the initial Therapeutic Dose,

The second Therapeutic Dose should be decreased to 425 mCi (or 7 mCi/kg for subjects weighing less than 62.5 kg).

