7.8. Subgroup Analyses

The following subgroups will be used for selected analysis including primary and additional efficacy analyses, overall survival and treatment-emergent adverse events:

- Number of therapeutic doses (0, 1 or 2).
- Baseline factors, such as location of metastases (lung and/or liver vs no lung or liver metastases).
- Any prior MIBG/Azedra treatment (yes or no) as recorded in the cancer history case report form.

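### The AESI table in SAP 7.5.8 is a late-onset figure, not total AESI incidence, and its window does not meet the other adverse-event windows at Week 16

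*SAP*

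**What the plan says.** - **AESI analysis.** SAP 7.5.8 states that AESIs "with an onset beyond 16 weeks after the last therapeutic dose of study drug will be summarized and reported in a separate listing". Its opening sentence attributes the 16-week limit to the protocol's definition.
- **AESI definition.** The defining sentence in Protocol 12.1.2.1 describes a type of event of concern with this drug and sets no time limit. The same section gives late radiation toxicity as the purpose and starts AESI reporting 16 weeks after the last therapeutic dose. Protocol 12 has the same start.
- **Site classification.** Protocol 12.1.4 covers "occurrence of adverse events from the time of informed consent until the Safety Phone Call 16 weeks after the last dose of study drug" and, for each such event, instructs the site: "Determine if the event is an AESI (see Appendix VI". No analysis in the SAP uses this early classification.
- **Treatment-emergent window.** SAP 7.5.1 runs from the first study drug "to the end of 15 weeks after the administration of the last therapeutic dose of iobenguane I 131". The SAE table in SAP 7.5.4 counts treatment-emergent SAEs only.
- **Late-event table.** SAP 7.5.1 also tabulates events starting on or after the first day of Week 16, but only those that are neither SAEs nor AESIs (Table 14.3.1.1.1).
- **Timing of dose 2.** Protocol 9.3 places it "at least 12 weeks after the first Therapeutic Dose", and Protocol 10.2 says "this delay of second therapeutic dose should not exceed 24 weeks from the first therapeutic dose". Not every subject gets two doses: one SAP 7.8 subgroup is "Number of therapeutic doses (0, 1 or 2".

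**The concern.** A table titled Adverse Events of Special Interest will be read as the frequency of radiation-type toxicity on the AESI list. Because the filter is on onset, an event that starts before the cut-off stays out however long it lasts. The cut-off runs from the last dose, so the uncovered period after dose 1 is longer for subjects who received more treatment.

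The second issue is the join between windows. Three rules with slightly different edges meet at Week 16, and an event starting there can miss every adverse-event summary table. What is at stake is the pooled AESI incidence in the study report. The primary endpoint is not affected.

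**Working it through.** **1. The plan's own figure.** Protocol 10.2.2 says that the second dose "may be delayed for up to 4 - 12 weeks (i.e., 16 - 24 weeks following administration of the first Therapeutic Dose". With the 12-week minimum from Protocol 9.3: 12 + 4 = 16 and 12 + 12 = 24 weeks. The figure is reproduced, and 24 agrees with the limit in Protocol 10.2.

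**2. When the AESI table starts counting.** Weeks after dose 1 = week of the last therapeutic dose + 16.

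| Last therapeutic dose | Window opens after | Share of first 52 weeks | Share of 5 years (5 × 52 = 260 weeks) |
|---|---|---|---|
| Dose 1 only | 0 + 16 = 16 weeks (Day 112) | 16/52 = 31% | 16/260 = 6% |
| Dose 2 at Week 12 | 12 + 16 = 28 weeks (Day 196) | 28/52 = 54% | 28/260 = 11% |
| Dose 2 at Week 24 | 24 + 16 = 40 weeks (Day 280) | 40/52 = 77% | 40/260 = 15% |

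These are shares of time, not of events. Protocol 7.1 says survival in this setting is often 24 months or less. If follow-up is assumed to be 104 weeks, the last column becomes 16/104 = 15%, 28/104 = 27% and 40/104 = 38%.

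**3. An example.** Myelodysplastic syndrome is a SAP Appendix 2 term. Suppose it starts on Day 182 after dose 1 (26 weeks). In a one-dose subject 26 > 16, so it is in the AESI table. In a two-dose subject 26 < 28 even with the earliest dose 2, so it is not.

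**4. The join at Week 16.** Protocol 11.5.18 ends Week 15 on Day 105 and makes Week 16 Days 106 to 112. Those days count from dose 1; the same week lengths are assumed here from the last dose.

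| Output | Onset covered, days after last dose | Serious AESI-term event, Day 106–112 |
|---|---|---|
| TEAE and grade 3/4 TEAE tables (SAP 7.5.1, 7.5.3) | to Day 105 (15 × 7) | not included |
| Treatment-emergent SAE table (SAP 7.5.4) | to Day 105 | not included |
| Late-event Table 14.3.1.1.1 | from Day 106, no SAEs or AESIs | not included |
| AESI Table 14.3.1.6 | after Day 112 (16 × 7) | not included |
| Listings of all AEs and all SAEs | no onset limit | included |

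A nonserious AESI-term event in Week 16 depends on which definition governs. Under the time-limited wording of SAP 7.5.8 it is not an AESI and can enter Table 14.3.1.1.1. If the site's classification under Protocol 12.1.4 counts, it is an AESI, is excluded there, and is untabulated too.

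Such events can be on file. Protocol 11.5.2, Protocol 12.1.4 and SAP 4.1 carry collection to 16 weeks after the last dose, although Protocol 12 and 12.1.2 stop routine collection at the last day of Week 15.

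**The case against.** The strongest reply is that the cut-off is the protocol's own. Protocol 12 and 12.1.2.1 separate routine adverse events from AESIs at about 16 weeks and give late radiation toxicity as the purpose. A table meant for late toxicity does not understate late toxicity by omitting early events. This stands: a reader might infer that the SAP departed from the protocol's reporting rule, and it did not. The conflict is between Protocol 12.1.4, which applies the AESI label from consent, and those two sections. The SAP adds to it by calling a reporting start a definition.

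A reader might also infer that early radiation toxicity goes unreported. The documents do not support that. Events through Week 15 after the last dose are tabulated by relatedness and grade and, where they qualify, as grade 3/4 or serious events. Laboratory outputs include CTCAE shift tables, hematologic nadir listings, a Hy's Law listing and a creatinine-clearance shift table. Scheduled thyroid testing after treatment and the dry-mouth evaluation are at Month 12 (Day 355 to 375), after even the latest opening of the AESI window (Day 280).

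What these outputs lack is a pooled count of early AESI terms. SAP 7.5.5 pools hematologic terms because similar events are coded differently, but its list has neither leukemia nor myelodysplastic syndrome, and no such pooling exists for the other early AESI terms.

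Last, adding early events brings in some acute ones. That is fair, and is a reason to split the table rather than move its cut-off.

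**Conclusion.** The point holds in a limited form. Table 14.3.1.6 and the AESI listings show late-onset events only and should not be read as total AESI incidence. The period not covered after dose 1 is 16 weeks for one-dose subjects and 28 to 40 weeks for two-dose subjects; the longer range does not apply to everyone. SAP 7.5.8 misdescribes the protocol's defining sentence, and the early site classification goes unused.

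A reader might turn the time shares into a percentage of AESIs missed. That would require a constant hazard and a known length of follow-up, and the documents supply neither. The share could be larger if onset is early or smaller if onset is late, so none is claimed.

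The gap at Week 16 is one week wide. It is clear for serious AESI-term events, which reach listings only. For nonserious ones it depends on the definition used. It rests on reading the SAP's limit literally as after Day 112; if the intent was from the first day of Week 16, the wording should say so.

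**What to change.** 1. In SAP 7.5.8, correct the definition sentence: the protocol defines AESIs by type of event and starts their reporting at 16 weeks after the last therapeutic dose. State how events classified earlier under Protocol 12.1.4 are handled.
2. In Table 14.3.1.6 and its listings, show SAP Appendix 2 terms with onset from the first therapeutic dose in two abutting columns plus a total: through the end of Week 15 after the last dose, and from the first day of Week 16 onward. Keep the late-onset column as the planned AESI result, noting that it now begins up to seven days earlier than a literal reading of the present text.
3. State whether the requirement to write up each AESI in the study report stays limited to late-onset events.

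The cost is small. The events and site classifications are already collected on the CRF. Site flags follow Protocol Appendix VI, which differs from SAP Appendix 2 (it includes headaches and hypertension, for example), so some mapping is needed. The total will be higher than the planned figure and will include some acute events, which the separate columns make visible.
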